7.5.1 Tumor Tissue Specimens

Pre-treatment tumor tissue specimens in the form of a paraffin embedded block or a minimum of 15 unstained slides will be submitted for PD-L1 IHC assessment. These biopsy samples should be from the most recent palliative surgery or biopsy. If surgical resection or biopsy are performed at one of the treatment sites, fresh tumor tissue for cell line establishment or fresh frozen tissue for tumor cell lysate will also be requested, but not mandated. Tumor specimens not used for clinical management will be utilized for research use. Approximately half of tumor tissue from biopsy or surgery will be stored as fresh frozen tissue for future IHC or preparation of tumor cell lysate. The remaining tumor will be sent directly to the PI's laboratory in order to establish cell line.

PD-L1 stained tissue sections will be assessed by a pathologist and membranous PD-L1 expression scored in tumor and immune cells if a minimum of a hundred (100) evaluable tumor cells are present. Subjects with positive, negative or indeterminate (membrane staining is obscured by high cytoplasmic staining or melanin content) IHC already has been well established at MCC tissue core for PD-L1. The cut-off for positive PD-L1 status was defined as IHC score > 2+ in more than 5% of tumor cells.

In addition, this pre-treatment tumor sample may be used to assess other putative predictive biomarkers of SBRT, nivolumab or ipilimumab efficacy and/or to better characterize the tumor-immune microenvironment post-resection. Of note, prior studies have suggest the expression of Merkel polyomavirus in tumor correlates with better responses to PD1 blockade³⁷. Therefore, Merkel polyomavirus large T antigen will be evaluated by IHC or viral load evaluated by qRT-PCR. Various other molecular markers with potential predictive value for the treatment of MCC with nivolumab, ipilimumab and other immunotherapies are currently under investigation and may be assessed in this study. These tumor tissue biomarkers include, but are not limited to PD-1, PD-L2, TILs or subpopulations of TILs and a Th1 immune mRNA expression signature. In addition, other methods of measuring tumor PD-L1 expression may also be assessed. Characterization of the tumor-immune microenvironment post-resection may involve assessment of other T cell checkpoint receptors and ligands (eg, Lag-3, Tim-3) and intratumoral immune cell subsets, including but not limited to NK cell, B-cell and T-cell lymphocytes.

Tumor tissue samples may also be collected during treatment, upon disease progression or completion of treatment. This second surgical resection or biopsy will be strongly recommended for correlative biomarker studies, but also not mandated. For lesions from active disease, fresh tumor may be used for cell line establishment. Otherwise, this sample may be used for preparation of tumor cell lysate for ex vivo recall responses, or for the assessment of markers implicated in resistance to immunotherapeutic agents, including but not limited to other T cell checkpoint receptors and ligands (eg, Lag-3, Tim-3) and intratumoral immune cell subsets, including but not limited to, T regulatory cells and myeloid derived suppressor cells. These samples may also be used to investigate the effect of nivolumab or ipilimumab the expression of potentially relevant predictive and/or prognostic MCC biomarkers, including, but not limited to BRAF mutation and PD-L1. Both the pre-treatment tumor sample and the sample collected upon recurrence may be retrospectively assessed for BRAF mutation status, as well as for the expression of other immune or MCC related genes, RNAs and/or proteins, or for the presence of immune cell populations using a variety of methodologies inclusive of, but not limited to IHC, qRT-PCR, genetic mutation detection and fluorescent in-situ hybridization (FISH).

7.5.2 Plasma Biomarkers

Blood samples for exploratory serum and plasma biomarker analyses will be drawn at the time points indicated in Section 7.1. Separate blood samples will be collected and processed for serum and plasma and then put in frozen storage. Serum and plasma samples may be assessed by ELISA, seromics, microRNA profiling, circulating tumor DNA measurements, metabolomics and/or other relevant multiplex-based protein assay methods for immune or Merkel cell carcinoma-related factors that will predict for SBRT, nivolumab or ipilimumab benefit or correlate with SBRT, nivolumab or ipilimumab-related adverse events. Numerous potential serum/plasma-based biomarkers are currently under investigation for their potential to predict or correlate with safety or efficacy to radiation therapy, nivolumab, ipilimumab or other immunotherapies, including but not limited to levels of soluble PD-L1, anti-tumor antibodies, cytokines, chemokines, inflammatory factors, NKG2D ligands (e.g., soluble MICA) and microRNAs (such as, but not limited to, miR-513 and miR19b). Plasma will be prepared along with PBMC.

7.5.3 Peripheral Blood Mononuclear Cells

Myeloid derived suppressor cells (MDSCs) and regulatory T cells (Tregs) are immune cell populations capable of suppressing T cell activation and proliferation. Low pre-treatment MDSC in peripheral blood may be associated with better overall survival in Merkel cell carcinoma patients treated with the immunotherapeutic agents. Peripheral blood samples will be taken prior to initiation of study therapy and at designated timepoints on-treatment (see Section 7.1 for additional details on the blood sample collection schedule) for PBMC and MDSC preparation. PBMC and MDSC samples may be retrospectively assessed for correlative research to dissect underlying mechanisms of immune activation or tolerance in MCC or to discover novel therapeutic targets to enhance anti-tumoral immune responses using a variety of methodologies inclusive of, but not limited to ex vivo culture, flow cytometry, IHC, qRT-PCR, genetic mutation detection and fluorescent in-situ hybridization (FISH). 15cc of whole blood will be collected at week 1, 2, 3, 7, 13 and 25. PBMC from blood will be prepared with Ficoll gradient prior to freezing for future flow cytometry and ex vivo culture studies. Plasma will be stored for plasma biomarker studies (Section 7.5.2). Additional 5cc of whole blood will be collected in Cytochex for flow cytometric analysis.

7.6 Outcomes Research Assessments

HRQoL will be assessed using the EORTC QLQ-C30. The EORTC QLQ-C30 is the most commonly used QoL instrument in skin cancer clinical studies. It is a 30-item instrument that has gained wide acceptance in oncology clinical studies. The EORTC QLQ-C30 comprises 6 functional scales (physical functioning, cognitive functioning, emotional functioning, social functioning and global quality of life) as well as nine symptom scales (fatigue, pain, nausea/vomiting, dyspnea, insomnia, appetite loss, constipation, diarrhea, and financial difficulties). Except for the overall health status and global quality of life items, responses for all items are 4 point categorical scales ranging from 0 (Not at all) to 4 (Very much). The overall health status/quality of life responses are 7-point Likert scales.

General health status will be measured using the EQ-5D. The EQ-5D is a standardized instrument for use as a measure of self-reported health status. The EQ-5D comprises 5 dimensions (mobility, self-care, usual activities, pain/discomfort and anxiety) and a visual analog rating scale (VAS). The EQ VAS records the respondent's self-rated health on a vertical, visual analogue scale where the endpoints are labeled 'Best imaginable health state' and 'Worst imaginable health

state'. This information can be used as a quantitative measure of health outcome as judged by the individual respondents. The utility data generated from the EQ-5D is recommended for and commonly used in cost effectiveness analysis.

Work Productivity and Activity Impairment: General Health (WPAI:GH) is a 6-item questionnaire yielding four different types of scores. The WPAI:GH was created as a patient-reported quantitative assessment of the amount of absenteeism (work time missed), presenteeism (impairment at work), work productivity (overall work impairment/absenteeism plus presenteeism) and daily activity impairment attributable to general health. WPAI:GH outcomes are expressed as impairment percentages, with higher numbers indicating greater impairment and less productivity, ie, worse outcomes. The recall period in all WPAI:GH validation studies is 7 days. The general literature on recall burden suggests that a longer recall period would not be suitable for the type of information being elicited in the WPAI:GH. In theory, a shorter recall period would improve accuracy of WPAI:GH responses, but this has not been tested. Assessment of work productivity will be conducted at each site (or remotely) with the appropriately translated and validated version of the WPAI:GH. All PRO instruments will be administered during on-study, and follow-up phases as outlined in Tables of Section 5.1, respectively, to all randomized subjects. Healthcare resource utilization data (eg, hospitalizations, non-protocol specified medical visits, diagnostics, etc) will be collected for all randomized subjects. The resource utilization capture is specific to hospital admission utilization data and non-protocol specified visits related to study therapy. Resource utilization questions will be asked as outlined in Table of Section 5.1 during screening, on-study, and follow-up phases, respectively.

An **Adverse Event (AE)** is defined as any new untoward medical occurrence or worsening of a preexisting medical condition in a clinical investigation subject administered study drug and that does not necessarily have a causal relationship with this treatment. An AE can therefore be any unfavorable and unintended sign (such as an abnormal laboratory finding), symptom, or disease temporally associated with the use of study drug, whether or not considered related to the study drug.

The causal relationship to study drug is determined by a physician and should be used to assess all adverse events (AE). The causal relationship can be one of the following:

Related: There is a reasonable causal relationship between study drug administration and the AE.

Not related: There is not a reasonable causal relationship between study drug administration and the AE.

The term "reasonable causal relationship" means there is evidence to suggest a causal relationship.

Adverse events can be spontaneously reported or elicited during open-ended questioning, examination, or evaluation of a subject. (In order to prevent reporting bias, subjects should not be questioned regarding the specific occurrence of one or more AEs.)

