**A Phase 2, Randomized, Multi-institutional Study of Nivolumab and Ipilimumab
versus Nivolumab, Ipilimumab and Stereotactic Body Radiation Therapy for
Metastatic Merkel Cell Carcinoma**

NCT03071406

Version 11

January 26, 2023

Clinical Protocol

A Phase 2, Randomized, Multi-institutional Study of Nivolumab and Ipilimumab versus Nivolumab, Ipilimumab and Stereotactic Body Radiation Therapy for Metastatic Merkel Cell Carcinoma

PI: [name], PhD

Co-PI: [name]

Co-Investigator: [name]

Co-Investigator: [name], PhD

Co-Investigator: [name]

Co-Investigator: [name]

Co-Investigator: [name]

Co-Investigator: [name], PhD

Biostatistician: [name]

Pathologist: [name]

Radiologist: [name]

OSU Site PI: [name]

Collaborating Institutions:

Ohio State University James Cancer Hospital and Solove Research Institute

DOCUMENT HISTORY

Document	Date of Issue	Summary of Change
Original Protocol		Not applicable

SYNOPSIS

Clinical Protocol

Protocol Title: A Phase 2, Randomized, Multi-institutional Study of Nivolumab and Ipilimumab versus Nivolumab, Ipilimumab and Stereotactic Body Radiation Therapy for Metastatic Merkel Cell Carcinoma.

Investigational Product(s), Dose and Mode of Administration, Duration of Treatment with Investigational Product(s):

Stereotactic Body Radiation Therapy 24Gy in 3 fractions.

Nivolumab 240 mg/dose IV q2 weeks.

Ipilimumab 1 mg/kg/dose IV q6 weeks.

Treat subjects until disease progression, unacceptable toxicity or subject withdrawal of consent.

Study Phase: 2

Research Hypothesis: Treatment with nivolumab and ipilimumab, or nivolumab and ipilimumab in combination with stereotactic body radiation therapy (SBRT) will improve objective response rate as compared to nivolumab alone historical control in subjects with metastatic Merkel cell carcinoma.

Objectives:

Primary:

- To compare the efficacy, as measured by objective response rate (ORR), provided by nivolumab plus ipilimumab with or without SBRT in subjects with metastatic Merkel cell carcinoma.

[figure not shown]
Secondary:

- To compare the progression free survival (PFS) of nivolumab and ipilimumab versus SBRT plus nivolumab and ipilimumab in subjects with metastatic Merkel cell carcinoma.
- To compare the overall survival (OS) of nivolumab and ipilimumab versus SBRT plus nivolumab and ipilimumab in subjects with metastatic Merkel cell carcinoma.
- To evaluate the local control of irradiated tumor provided by SBRT in combination with nivolumab and ipilimumab

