- All subjects must be either recurrent, unresectable or Stage IV AJCC (7th edition) and have histologically confirmed Merkel cell carcinoma with at least 2 distinct lesions in order to be eligible. Please refer to [Appendix 1](#) for description of AJCC 7th editions of TNM and staging.

- All subjects must have at least 2 distinct lesions as documented by a complete physical examination or imaging studies within 4 weeks prior to randomization. Imaging studies must include a diagnostic CT scan of the involved disease sites and all known sites of resected disease and brain magnetic resonance (MRI) or CT (brain CT allowable if MRI is contraindicated or if there is no known history of resected brain lesions).
- Tumor tissue from the core biopsy or resected site of disease must be provided for biomarker analyses.

Key Exclusion Criteria:

- Subjects with history of Grade 3 toxicity or use of infliximab with prior immunotherapy
- Patients with active brain metastasis.
- Subjects with active, known, or suspected autoimmune disease. Subjects with type I diabetes mellitus, residual hypothyroidism due to autoimmune thyroiditis only requiring hormone replacement, skin disorders (such as vitiligo, psoriasis, or alopecia) not requiring systemic treatment are permitted to enroll.
- Subjects with prior history of non-Merkel cell carcinoma malignancies are excluded except adequately treated basal cell, squamous cell skin cancer, chronic lymphocytic leukemia or other indolent diseases not requiring therapy; adequately treated, with curative intent, cancer from which the patient is currently in complete remission per investigator’s judgment; or patients with history of breast cancer and no evidence of disease on hormonal therapy to prevent recurrence and patients with prostate cancer on adjuvant hormonal therapy with undetectable PSA are eligible.
- Subjects with a condition requiring systemic treatment with either corticosteroids (> 10 mg daily prednisone equivalent) or other immunosuppressive medications within 14 days of randomization. Inhaled or topical steroids are permitted in the absence of active autoimmune disease.

Study Drug:

Study Drug		
Medication	Potency	IP/Non-IP
Nivolumab Solution for Injection	100 mg (10 mg/mL)	IP
Ipilimumab Solution for Injection	50 mg (5 mg/mL)	IP

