5.1 Investigational Product

An investigational product, also known as investigational medicinal product in some regions, is defined a pharmaceutical form of an active substance or placebo being tested or used as a reference in a clinical study, including products already with a marketing authorization but used or assembled (formulated or packaged) differently than the authorized form, or used for an unauthorized indication, or when used to gain further information about the authorized form.

The investigational product should be stored in a secure area according to local regulations. It is the responsibility of the investigator to ensure that investigational product is only dispensed to study subjects. The investigational product must be dispensed only from official study sites by authorized personnel according to local regulations.

In this protocol, investigational products are: nivolumab and ipilimumab.

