6.8 Radiation Therapy Adverse Events

All Radiation Therapy AEs will be scored according to the NCI Common Terminology Criteria for Adverse Events (CTCAE) version 4. Adverse events related to SBRT for the treatment of metastases are dependent on the location of the metastases treated as well as from exposure of surrounding normal tissues. For all treated metastases, fatigue may occur and should be transient lasting < 8 weeks. Other adverse events are likely to be related to the specific metastatic location receiving SBRT:

Lung (Central and Peripheral), Mediastinal, Head and Neck Metastases:

Cardiac and Pericardial Injury

Although cardiac and pericardial injury is uncommon in the conventionally fractionated course of RT, with large doses per fraction of SBRT a number of possible side-effects can be seen.

Esophageal/Pharynx/Oral Cavity/Salivary gland Injury

The radiation effects on the oral cavity, pharynx and esophagus can be acute: esophagitis (i.e., dysphagia, causing pain on swallowing, typically relatively soon after RT course is completed, and typically resolves on its own within days to a week or longer), mucositis, altered taste, xerostomia or chronic, typically manifesting with persistence of acute symptoms, dysphagia due to stenosis, or esophageal ulceration, with perforation in the extreme cases.

Brain/Brainstem/Optic apparatus/Cochlea Injury

The radiation effects on the CNS includes visual disturbances, auditory disturbances, memory problems, and radiation necrosis. While these are rare toxicities, radiation planning should ensure avoidance of the critical structures during SBRT.

Central Airway/Bronchial Injury

This bronchial injury with subsequent focal collapse of lung may impair overall pulmonary status. It also makes further assessment of tumor response more difficult as the collapsed lung approximates the treated tumor. Because atelectatic lung and tumor have similar imaging characteristics, radiology reports will often describe the overall process as progressive disease while the actual tumor may be stable or shrinking.

The consequences of bronchial toxicity, e.g., cough, dyspnea, hypoxia, impairment of pulmonary

function test parameters, pleural effusion or pleuritic pain (associated with collapse), should all be graded according to the Common Terminology Criteria for Adverse Events (CTCAE), v. 4; MedDRA, v. 12.0.

Lung Injury

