8.1.1 Serious Adverse Event Collection and Reporting

Sections 5.6.1 and 5.6.2 in the Investigator Brochure (IB) represent the Reference Safety Information to determine expectedness of serious adverse events for expedited reporting. Following the subject's or the legal representative's written consent to participate in the study, all SAEs, whether related or not related to study drug, must be collected, including those thought to be associated with protocol-specified procedures. All SAEs must be collected that occur during the screening period and within 100 days of discontinuation of dosing. If applicable, SAEs must be collected that relate to any later protocol-specified procedure (eg. a follow-up skin biopsy).

The investigator should report any SAE that occurs after these time periods and that is believed to be related to study drug or protocol-specified procedure.

An SAE report should be completed for any event where doubt exists regarding its seriousness.

If the investigator believes that an SAE is not related to study drug, but is potentially related to the conditions of the study (such as withdrawal of previous therapy or a complication of a study procedure), the relationship should be specified in the narrative section of the SAE Report Form.

SAEs, whether related or not related to study drug, and pregnancies must be reported to BMS (or designee) within 24 hours. SAEs must be recorded on the SAE Report Form; pregnancies on a Pregnancy Surveillance Form (electronic or paper forms). The preferred method for SAE data reporting collection is through the eCRF. The paper SAE/pregnancy surveillance forms are only intended as a back-up option when the eCRF system is not functioning. In this case, the paper forms are to be transmitted via email or confirmed facsimile (fax) transmission to:

SAE Email Address: [contact]

SAE [contact]

For studies capturing SAEs/pregnancies through electronic data capture (EDC), electronic submission is the required method for reporting. The paper forms should be used and submitted immediately, only in the event the electronic system is unavailable for transmission. When paper forms are used, the original paper forms are to remain on site.

If only limited information is initially available, follow-up reports are required. (Note: Follow-up SAE reports should include the same investigator term(s) initially reported.)

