9.1.2 Populations for Analyses

- All enrolled subjects: All subjects who signed an informed consent form and were registered.
- All randomized subjects: All subjects who were randomized to any treatment arm in the study.
- All treated subjects: All subjects who received any study drug nivolumab, ipilimumab or SBRT.
- Biomarker subjects: All randomized subjects with available biomarker data (PD-L1 expression status, Merkel cell polyomavirus expression, and other assays).

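### AE causality is rated only against an inconsistently used term, study drug, so an SBRT-caused event can be coded not related; separately, the interim SBRT safety criterion, read literally, covers three diagnoses

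*Combined protocol and SAP*

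**What the plan says.** **Causality.** The definitions that open the adverse event material (Section 8, printed directly after 7.6) ask a physician to rate every AE against study drug in one of two categories: "Related: There is a reasonable causal relationship between study drug administration and the AE" and "Not related: There is not a reasonable causal relationship between study drug administration and the AE".

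**What study drug covers.**
- SBRT left out: the synopsis Study Drug table has two entries, nivolumab and "Ipilimumab Solution for Injection". Section 5.1 states "In this protocol, investigational products are: nivolumab and ipilimumab". The dose-delay rule in 5.5.5 mentions attribution to nivolumab, ipilimumab or both.
- SBRT included: the synopsis list of investigational products opens with "Stereotactic Body Radiation Therapy 24Gy in 3 fractions". Table 7.1-2 enters RT at Week 2 in the treatment row under the Study Drug heading. Section 9.1.2 defines treated subjects as "All subjects who received any study drug nivolumab, ipilimumab or SBRT".

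**Recording of radiation events.** Section 6.8 says "All Radiation Therapy AEs will be scored according to the NCI Common Terminology Criteria for Adverse Events (CTCAE) version 4". Section 8.1.1 says "all SAEs, whether related or not related to study drug, must be collected, including those thought to be associated with protocol-specified procedures"; where an SAE is judged unrelated to drug but possibly due to a study procedure, that relationship goes in the SAE narrative.

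**Analysis.** Section 9.3.3 tabulates all on-study AEs and SAEs, and also treatment-related AEs and SAEs, by arm. It does not define treatment-related.

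**Interim criterion.** The synopsis and Section 4.1 (Stopping criteria) ask, after the first Simon stage accrues, whether SBRT adds an excess of unanticipated Grade 3 or higher toxicity. An i.e. then introduces radiation pneumonitis, dermatitis and myelitis. No number defines an excess.

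**The concern.** SBRT is what distinguishes Arm B from Arm A, and comparing the safety of the two arms is a secondary objective (1.3.2). A reader wanting to know what SBRT itself adds will turn to the treatment-related tables. If SBRT-caused events are coded not related, those tables understate Arm B, and two investigators following the same protocol could code the same radiation injury differently.

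The interim criterion is the only written SBRT-specific test before the cohorts expand. Taken at its word, it does not require the reviewers to count a Grade 3 or higher radiation injury of the liver, bowel or esophagus.

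**Working it through.** No figure in the plan is in dispute, so the main check sets the passages side by side.

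**1. Coding of an SBRT-caused AE under each reading**

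| Reading of study drug | Code | Consequence |
|---|---|---|
| Nivolumab and ipilimumab only (synopsis table, 5.1, 5.5.5) | Not related | Missing from the treatment-related tables |
| SBRT included (synopsis product list, Table 7.1-2, 9.1.2) | Related | Counted, but not separable from a drug-caused event |

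Neither reading yields a coded SBRT attribution.

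**2. Whether another provision supplies one**
- Section 6.8 supplies a severity grade, not relatedness.
- Section 8.1.1 supplies narrative text, for SAEs only.
- Treatment-related in 9.3.3 could be read to include SBRT (6.1.1 uses the phrase of radiation), but no coded rating described in the protocol supports that reading.

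**3. What does not depend on the code**
- All on-study AEs and SAEs by arm (9.3.3).
- The safety endpoint, which is incidence (9.2.2).
- The between-arm chi-square comparison of toxicity (synopsis, Analyses).

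**4. Interim criterion against Section 6.8**
- Named in the criterion: pneumonitis, dermatitis, myelitis.
- Described in 6.8 but not named: radiation-induced liver disease, which 6.8 says can end in liver failure and death; ulceration, bleeding, fistula or obstruction of the bowel; esophageal ulceration, with perforation in extreme cases.
- The word unanticipated is unsettled. Section 6.1.1 expects no treatment-related toxicity, while 6.2.1 notes a potentially increased pneumonitis risk and 6.8 describes all three named effects.

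**5. Would an all-cause comparison by arm be enough at the interim?**
Inputs: 16 patients per arm (9.1.1). The assumed background Grade 3–4 rate is 10/54 = 18.5%, taken from the treatment-related events in the lung cancer cohort on nivolumab 3 mg/kg plus ipilimumab 1 mg/kg (1.5.4). The assumed SBRT excess is 2/16 = 12.5 points, so Arm B is at 18.5% + 12.5% = 31.0%. The test is one-sided Fisher at 10%.

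Power = sum of Bin(a; 16, 0.185) × Bin(b; 16, 0.310) over all pairs (a, b) with Fisher p ≤ 0.10, which is about 19%.

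For contrast, the chance that 16 Arm B patients show at least one SBRT-caused event is 1 − (1 − q)^16. The documents give no q, so a range is assumed:

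| True rate q | P(at least one in 16) |
|---|---|
| 2% | 28% |
| 5% | 56% |
| 10% | 82% |
| 20% | 97% |

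An unattributed comparison at this size would usually miss a moderate excess. Event-by-event review of possible SBRT relatedness has more chance of raising a question, although one event does not establish an excess.

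**The case against.** The strongest reply is that little depends on the code. Section 9.3.3 analyses treated subjects, whom 9.1.2 defines with SBRT included. The AE rows of the schedule point to Sections 6.8 and 8 together. Section 8.1.1 also asks for later SAEs believed related to a study procedure. The bar for related is low, and pneumonitis on nivolumab would plausibly be coded related anyway. The AE form is not in the documents and may already hold an SBRT field. All of this stands. It reduces the likely impact, but it does not give the protocol a coded SBRT rating or a definition of treatment-related.

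On the interim criterion, excluding everything 6.8 describes would exclude the three diagnoses the criterion itself names, so that cannot be the intent; and i.e. may be a slip for e.g. The Safety Monitoring Committee evaluates toxicity in both arms, the Protocol Monitoring Committee reviews all AEs monthly (8.8), and 1.6 names a data safety monitoring committee. That stands too: oversight as a whole is wider than the criterion. But none of these bodies is given an SBRT criterion of its own, and if the wording is a slip it should be corrected.

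Four stronger readings are tempting but unsupported:
- *SBRT toxicity goes unrecorded, or the safety comparison is biased.* Events are collected and graded, and the all-cause comparison does not use attribution.
- *The short diagnosis list measures uncovered risk.* Setting it against the organs in Table 6.5.5-1 shows only narrow wording; those organs are not equally likely to be injured or even irradiated.
- *Patients with radiation injury would be denied steroids.* Section 4.2.1 exempts only drug-related events, but 4.2.2 allows a brief course for non-autoimmune conditions and 6.8 directs steroids for significant pneumonitis and for myelitis.
- *The mandatory pneumonitis discontinuation rule should extend to SBRT-caused events.* That would stop both drugs in Arm B only and could affect efficacy. Sections 4.3, 5.5.5 and 5.5.7 already leave such events to the investigator's judgment.

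**Conclusion.** The point holds as a cheap improvement. As written, an SBRT-caused AE can be coded not related, and on either reading of study drug it cannot be separated from a drug effect. The descriptive treatment-related tables can therefore understate Arm B. The effect on the all-cause tables, the incidence endpoint and the between-arm test is zero. The interim criterion, read literally, is narrower than the serious injuries the protocol itself describes; committee oversight reduces that gap but does not replace the criterion.

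No count of affected patients can be given. The documents state no SBRT event rate at 24 Gy in 3 fractions, and the AE form was not available. The 19% power figure rests on an assumed background from another tumour and an assumed excess; it bears only on the choice of remedy.

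**What to change.** 1. **Attribution.** Define study treatment once as nivolumab, ipilimumab and SBRT. For every AE, record relatedness to immunotherapy and to SBRT separately. In 9.3.3, define treatment-related as related to any of the three.
2. **Interim criterion (synopsis and 4.1).** Delete unanticipated and change i.e. to e.g. Have the committee review every Grade 3 or higher event at least possibly related to SBRT, whatever the diagnosis. Show all Grade 3 or higher AEs by arm as supporting information, not as the sole test.
3. **Optional.** Align the steroid exemption in 4.2.1 with 6.8.

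The cost is protocol wording and one field on the AE form, if it is not already there; no extra patients or procedures. Arm B's stated treatment-related rate may rise. If the stage 1 review has already taken place, item 1 can still be done from source documents before the final tables.
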